9.3 POPULATIONS FOR ANALYSES

Every effort will be made to ensure all enrolled and randomized participants complete all study sessions as described in this protocol. However, *a priori*, we determine that our population for analysis will be a per-protocol analysis dataset, indicating that only those who complete the intervention (i.e., the 5 days of stimulation) will be included in the analysis. For this study, enrolled eligible participants will be randomized to receive 5 consecutive days of stimulation. If a participant completes the intervention (i.e., receives all 5 consecutive days of stimulation), they will be included in all analyses moving forward.

Reasons for missing data (e.g., missing follow-up sessions) and reasons for participant withdrawal will be documented within the master list.

As stated previously in *Section 7 Study Intervention Discontinuation and Participant Discontinuation/Withdrawal*, enrolled participants who do not complete the full intervention will not be included in this analysis. Therefore, with this population for analysis plan, we anticipate having data from at least 45 participants that are eligible for analysis.

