9.4.2 ANALYSIS OF THE PRIMARY EFFICACY OUTCOME MEASURE(S)

We will perform spectral analysis of resting state EEG from day 1 of stimulation (baseline) to day 5 of stimulation. We will use a general linear mixed-effects model (GLMM) to assess if there is statistically significant interaction between treatment (sham/placebo, theta-tACS and alpha-tACS) and session (baseline/Day 1 of stimulation, day 5 of stimulation, 2-week follow-up, 4-week follow-up). Spectral analysis will be performed with multitapered estimation of the frequency spectrum followed by integration over the classical alpha EEG band (usually 8-12 Hz). In a separate analysis, we will perform spectral analysis of resting state EEG before and after each separate stimulation session. These analyses will be completed on the per-protocol dataset.

In our previous study, which used a 5-day protocol in patients with depression (Alexander et al., 2019), we found that a correlation between the log-transformed baseline alpha power (dB) and the alpha power changes at the end of the intervention (Day 5) in all regions. We chose to use the log-transformed baseline alpha power as a covariate. We will use this same covariate in these analyses as well.

Results from this section will be described in mean decibel (dB) change and presented using spectral images for visualization.

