9.4.4 SAFETY ANALYSES

Safety will be assessed with a suicide questionnaire, the Columbia-Suicide Severity Rating Scale (C-SSRS), an adverse effects questionnaire, and the Young Mania Rating Scale (YMRS).

The suicide questionnaire is used as a screening to assess increase in suicidal ideation (SI) or suicidal behavior (SB). If a participant's responses indicate SI or SB, the participant will be contacted and an acute assessment will be completed if necessary by [name]. Any verified increases in suicidal ideation will be described in counts/percentages and compared between groups using chi-square tests.

The adverse effects questionnaire will be administered following every stimulation session, for a total of 5 administrations per participant. The adverse effects questionnaire inquires about 14 possible adverse effects associated with electrical stimulation, rated on a scale of 1 (absent) to 4 (severe). Paired t-tests

with random effect "participant" will be calculated per adverse effect to determine if there are any differences in adverse effect severity between groups (sham/placebo, alpha-tACS, theta-tACS). Severity per adverse effect will be described with mean and standard deviation.

The Young Mania Rating Scale (YMRS) will be used to assess any development of mania over the course of treatment. A YMRS score of greater than 12 indicates the possible development of a manic episode. Any participant who scores greater than 12 on the YMRS will be assessed by [name]. Any verified manic episode will be described in counts/percentages and compared between groups using a chi-square test.

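### No safety population is defined: read literally, Section 9.3 drops participants stopped early from the final between-arm safety comparison, and the paired t-tests in Section 9.4.4 cannot compare three parallel arms

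*Combined protocol and SAP*

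**What the plan says.** Section 9.3 is the only section on analysis populations. It adopts a per-protocol dataset, in which "only those who complete the intervention (i.e., the 5 days of stimulation) will be included in the analysis", and repeats that "enrolled participants who do not complete the full intervention will not be included in this analysis". Section 9.4.2 applies this set to the primary outcome: "These analyses will be completed on the per-protocol dataset".

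Section 9.4.4 has no matching sentence. On suicidal ideation it says: "Any verified increases in suicidal ideation will be described in counts/percentages and compared between groups using chi-square tests". Verified manic episodes are treated the same way. The side-effect questionnaire is given after every stimulation session, "for a total of 5 administrations per participant". Its items are "rated on a scale of 1 (absent) to 4 (severe). Paired t-tests" and, as the sentence continues, "with random effect 'participant' will be calculated per adverse effect to determine if there are any differences in adverse effect severity between groups", the groups being sham, alpha-tACS and theta-tACS.

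Section 7.1 ends stimulation for increased suicidal risk, a YMRS score above 12, or an adverse event that makes continuing unwise. Section 8.2.1 ends participation on a report of suicidal ideation or behaviour, or on mania in the stimulation week. Section 7.2 replaces participants who leave after partial treatment, and Section 6.2.1 reassigns their randomization codes.

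**The concern.** The safety events to be compared are among the reasons for leaving the only population the plan defines. If that population serves as the safety denominator, a participant whose ideation or mania stops stimulation on, say, Day 3 is missing from both numerator and denominator of the final table. That is selection on the outcome.

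The harm in question is one the protocol itself raises. Section 2.3.1 says theta-tACS could in theory worsen depression. It also reports a similar trial in which suicidal thoughts increased in 4 sham participants and in none on tACS. Section 9.2 counts tolerability information and interval estimates among the most important products of this pilot. As the text stands, two analysts could follow it and report different denominators.

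The second defect does not depend on how Section 9.3 is read: the side-effect comparison cannot be run as worded.

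**Working it through.** **Denominator: the passages side by side**

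- For completers only: Section 9.3 offers no other set and makes no exception for safety. The count of 5 questionnaires per participant in Section 9.4.4 is true only of someone who had all 5 sessions; a participant stopped after session 2 contributes 2.
- For everyone treated: only Section 9.4.2 names the per-protocol dataset, and Section 9.4.4 speaks of any verified event.
- Neither side states a rule for safety.

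**How much could be lost**

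The plan gives no event rates or timing, so all of this is illustration. Let R be the cumulative risk of a first event from first stimulation to the 4-week visit. R = 5% to 25% is assumed; the upper value is the figure for ideation in SLE patients in Section 2.2, used only as a bound. With m equal-risk units, k of them before session 5 is complete, and every positive answer ending participation:

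h = 1 - (1 - R)^(1/m); share leaving the completer set = [1 - (1 - h)^k] / R.

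*Equal risk per questionnaire.* Section 8.2.1 uses the suicide questionnaire at each session, covering the past 24 hours. If it is asked before stimulation, the later assessments are Days 2-5 and two follow-ups, so k = 4 and m = 6. If it is asked after, they are Days 1-5 and two follow-ups, so k = 4 and m = 7.

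- Lowest (R = 0.05, m = 7): h = 0.00730; 0.02889 / 0.05 = 57.8%.
- Highest (R = 0.25, m = 6): h = 0.04682; 0.17452 / 0.25 = 69.8%.

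*Equal risk per day.* The schedule puts the 4-week visit at day 33, so m = 32 or 33 and k = 4 or 5.

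- Lowest (R = 0.05, k = 4, m = 33): 0.00620 / 0.05 = 12.4%.
- Highest (R = 0.25, k = 5, m = 32): 0.04396 / 0.25 = 17.6%.

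*Only half of positive answers lead to a stop.* Replacing h by h/2 in the bracket gives 29-36% per questionnaire and 6-9% per day.

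*In counts.* With 4 events in all (the number Section 2.3.1 reports for the similar trial), the expected number lost is 4 x 0.124 to 4 x 0.176, or 0.5 to 0.7, per day; and 4 x 0.578 to 4 x 0.698, or 2.3 to 2.8, per questionnaire.

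**The test**

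- A paired t-test analyses differences within matched pairs. Section 4.1 assigns each participant to one of three arms, so there are no between-arm pairs.
- One paired test covers two conditions, and there are three arms.
- A paired t-test has no random-effect term. Naming participant as a random effect over repeated sessions describes a mixed model, which is probably what was meant.

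**The case against.** The best case for the plan is that Section 9.3 was written with efficacy in mind. It says completers enter all analyses, which does not strictly say that nobody else does, and its exclusions refer to the analysis in the singular. Section 9.4.4 refers to any verified event and looks for mania over the course of treatment; since mania stops stimulation, a completer-only comparison would have almost nothing to show from that week. The 5 administrations may simply describe the schedule. This stands as far as it goes: an inclusive reading is open, and a reader should not infer that the sponsor has decided to exclude early stoppers. But the text does not adopt that reading either.

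A reader might also infer that these events vanish from the trial. They do not. Section 8.3.4 records all adverse events. Section 7.1 follows those who stop early to week 4 with HDRS, YMRS and the suicide questionnaire. The stopping rules in Section 7.4 count against enrollment. The DSMB receives safety summaries every 6 months and can see them by arm if there is reason (Section 9.4.6). None of this places early stoppers in the final by-arm comparison.

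Three further inferences are not supported:

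- That a significant arm difference would be hidden. One can choose event patterns for which a small p-value disappears among completers, but the result depends on putting all events in one arm and most of them early. With events spread over the arms, neither set shows a difference.
- That stopping for severe discomfort (Section 2.3.1) removes the worst side-effect scores. The passage stops the stimulation but does not cancel later sessions, so this is only a possibility.
- That the paired t-test would inflate false positives. That would require pairing session records arbitrarily across arms, which nobody proposes.

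**Conclusion.** Both defects are in the text and should be corrected before the final analysis. The safety denominator is undefined, and the only population on offer loses participants because of the events being compared. The named side-effect test does not fit the design.

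The possible loss is limited to the final by-arm safety analysis, and its size is uncertain: about 12-18% of participants with an event under equal daily risk, 58-70% under equal risk per questionnaire, and less if only some positive answers end participation. These ranges rest on assumed cumulative risks of 5-25% and on the timing assumptions above. The case for change does not depend on them, nor on any significance test. What is gained is complete counts and honest intervals, not power.

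**What to change.** 1. In Section 9.3, define a safety set of all participants who received any stimulation, analysed by stimulation received. Link records by participant ID, because Section 6.2.1 reuses randomization codes.
2. In Section 9.4.4, state that all safety analyses use this set, including whatever follow-up exists after an early stop, and report the number contributing per arm and session.
3. Replace the paired t-tests with a linear or ordinal mixed model for each item, with arm and session as fixed effects and participant as a random effect. It accepts fewer than 5 questionnaires per participant.
4. Report ideation and mania as counts per arm with exact confidence intervals; a between-arm test is optional.

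The cost is wording in two sections and slightly more analysis work. Follow-up will be incomplete for some early stoppers: Section 7.1 does not list the C-SSRS for them and leaves other measures to judgement, and Section 7.2 ends study participation on overlapping adverse-event grounds.

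A separate clinical-management point follows. Sections 2.3.1, 7.1, 8.2.1 and 9.4.4 differ on what follows a positive suicide-risk answer: Section 8.2.1 stops participation at once, while in Section 9.4.4 "the participant will be contacted and an acute assessment will be completed if necessary". Sections 7.1 and 8.2.1 differ on a YMRS score above 12. These passages must be reconciled, since they determine who leaves the completer set; no rule is proposed here.

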7 STUDY INTERVENTION DISCONTINUATION AND PARTICIPANT DISCONTINUATION/WITHDRAWAL

7.1 DISCONTINUATION OF STUDY INTERVENTION

Discontinuation from the week of stimulation does not mean discontinuation from the study, and remaining study procedures should be completed as indicated by the study protocol. If a clinically significant finding is identified (including, but not limited to changes from baseline) after enrollment, the investigator or qualified designee will determine if any change in participant management is needed. Any new clinically relevant finding will be reported as an adverse event (AE).

The study intervention (i.e., the 5 consecutive days of stimulation) will be discontinued for the following reasons:

- A participant develops increased suicidal risk, as determined by an acute assessment by [name].
- A participant has a YMRS score greater than to 12.
- The participant misses two consecutive days of stimulation.
- The participant misses a single day of stimulation and is unable to make it up at the end of the stimulation week.
- Any clinical adverse event (AE), laboratory abnormality, intercurrent illness or other medical condition, or situation occurs such that continued participation in the study would not be in the best interest of the participant.
- The participant meets any exclusion criteria (either newly developed or not previously recognized).
- A participant wishes to withdraw from further participation for any reason.

If the participant withdraws from the intervention, he/she will be followed through the 4 week follow-up with the designated clinical assessments to ensure participant safety:

- HDRS
- YMRS
- Suicide Questionnaire

Additional measures may be continued if deemed appropriate (e.g., EEG, cognitive tasks, Comparative Pain Scale, Pain Catastrophizing Scale).

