7.2 PARTICIPANT DISCONTINUATION/WITHDRAWAL FROM THE STUDY

A study participant will be discontinued from further participation if:

- Any clinical adverse event (AE), serious adverse event (SAE), laboratory abnormality, intercurrent illness or other medical condition, or situation occurs such that continued participation in the study would not be in the best interest of the participant.
- The participant meets any exclusion criteria (either newly developed or not previously recognized).
- A participant wishes to withdraw from further participation for any reason.

The reason for participant discontinuation or withdrawal from the study will be recorded with the participant files. Participants who sign the informed consent form and are not randomized will be replaced. Participants who sign the informed consent form, and are randomized and receive the full study intervention (5 consecutive days of 40 minutes of stimulation), and subsequently withdraw or are withdrawn or discontinue from the study will not be replaced. However, participants who sign the informed consent form, and are randomized and receive only part of the study intervention, and subsequently withdraw or are withdrawn or discontinue from the study will be replaced.

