8.2 SAFETY AND OTHER ASSESSMENTS

8.2.1 SAFETY

1. A suicide questionnaire previously used in IRBs #14-0600 and #14-1622 will be used at each session of this study. This questionnaire tracks suicidal ideation and behavior. Participants will be asked to answer whether they have had any thoughts of hurting themselves within the past 24 hours (suicidal ideation, SI) and whether they have hurt themselves within the past 24 hours (suicidal behavior, SB). If a participant admits to experiencing either SI or SB their participation will be stopped immediately and their primary mental health care provider or family physician will be contacted. In the case that they do not see anyone for their depressive symptoms, [name] will assist the participant in seeking medical care
2. The structural MRI to be used for source localization during EEG analysis will be conducted prior to randomization. The results of the T1 weighted sMRI will be reviewed by [name] for incidental findings of malignancy. If any are found, the study team will disqualify patient from study participation and will facilitate contact with providers for medical care per [name] recommendations. Patients will complete the provided MRI screening form provided by the Biological Research Imaging Center (BRIC) prior to the sMRI screening visit.
3. A stimulation adverse effects questionnaire will be administered at the end of each stimulation session. This questionnaire will be used as a safety measure and to collect data on participant experience. This questionnaire has been used in all our previous tACS studies.

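### Section 9.3 limits analysis to completers of all five sessions with no exception for safety, so, read as written, an event that stops stimulation early is left out of the arm comparison of that event

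*Combined protocol and SAP*

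**What the plan says.** **Population.** Section 9.3 defines one analysis set, called per-protocol: "only those who complete the intervention (i.e., the 5 days of stimulation) will be included in the analysis". Of completers it adds that "they will be included in all analyses moving forward", and it repeats that people who do not finish the intervention are not included. No safety set or all-treated set is defined anywhere. Section 9.4.2, on the primary EEG outcome, names its set: "These analyses will be completed on the per-protocol dataset". Section 9.4.4 has no matching sentence.

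**Safety comparisons.** On suicidality, Section 9.4.4 says: "Any verified increases in suicidal ideation will be described in counts/percentages and compared between groups using chi-square tests". It treats verified manic episodes the same way. It also compares side-effect severity between arms from a questionnaire that it expects to be given five times per participant.

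**Reasons for stopping.** Section 8.2.1, on the questionnaire used at each session, says: "If a participant admits to experiencing either SI or SB their participation will be stopped immediately". The list in Section 7.1 of reasons to stop stimulation includes "A participant develops increased suicidal risk, as determined by an acute assessment", a YMRS score above 12, and an adverse event that makes continuing against the participant's interest.

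**After stopping.** Under Section 7.1, a participant who leaves the intervention is still observed: "he/she will be followed through the 4 week follow-up with the designated clinical assessments" (HDRS, YMRS and suicide questionnaire). Under Section 7.2, participants who were "randomized and receive only part of the study intervention, and subsequently withdraw or are withdrawn or discontinue from the study will be replaced". Section 6.2.1 reassigns the device code of anyone who withdraws.

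**The concern.** The outcomes that Section 9.4.4 compares are largely the outcomes that end stimulation. If membership of the analysis set depends on finishing all five sessions, the event itself removes the participant from the set in which the event is counted. The comparison then describes only people who tolerated the full course. The stopped participant's side-effect scores leave with them.

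Section 9.2 counts tolerability among the main things the study is meant to deliver, and Section 2.3.1 says theta-tACS could in theory make depression worse. An event that stops stimulation during the treatment week is therefore one that most needs comparing between arms. The data would exist, because Section 7.1 keeps following these participants and Section 8.3.4 records all adverse events.

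Separately, the final analysis plans no by-arm summary of recorded AEs, SAEs or TEAEs that could fill the gap.

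**Working it through.** The plan gives no safety rate to reproduce, so the check is first of the text and then of what the rule would do to a proportion.

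**1. Text.**
- Who is analysed: 9.3, completers only, not limited to efficacy.
- Which set 9.4.4 uses: not stated, so 9.3 is the only rule on the page.
- Which events stop stimulation: suicidal ideation or behavior (8.2.1); increased suicidal risk, YMRS above 12 or an adverse event (7.1).
- Result: a verified event that stops stimulation before the fifth session is excluded. One that occurs in a completer after the fifth session is counted.

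**2. Effect on one arm's rate.** Let p be the true risk among all stimulated and f the share of events that stop stimulation early. Assuming nobody stops for another reason, the rate among completers is p(1 − f)/(1 − pf).

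| p | f=25% | f=50% | f=75% | f=100% |
|---|---|---|---|---|
| 5% | 3.8% | 2.6% | 1.3% | 0% |
| 10% | 7.7% | 5.3% | 2.7% | 0% |
| 20% | 15.8% | 11.1% | 5.9% | 0% |

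For example, with p=10% and f=50%: 0.10 × 0.50 / (1 − 0.05) = 5.3%.

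**3. The same in counts.** Section 9.3 expects at least 45 evaluable participants, or 45/3 = 15 per arm if balanced. Suppose 19 people in one arm are stimulated and 4 have a verified event. If 0, 1, 2, 3 or 4 of those four are stopped early, completers show (exact 95% intervals):
- 0 stopped: 4/19 = 21.1% (6.1 to 45.6%)
- 1 stopped: 3/18 = 16.7% (3.6 to 41.4%)
- 2 stopped: 2/17 = 11.8% (1.5 to 36.4%)
- 3 stopped: 1/16 = 6.3% (0.2 to 30.2%)
- 4 stopped: 0/15 = 0% (0 to 21.8%)

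**4. Effect on the planned test.** Take k early-stopping events in one arm (k of 15 + k stimulated) and 0/15 in each of the other two. Pearson chi-square on 2 degrees of freedom has p = exp(−X²/2). Among all stimulated:
- k=1: X² = 1.92, p = 0.38
- k=2: X² = 3.69, p = 0.16
- k=3: X² = 5.33, p = 0.069
- k=4: X² = 6.88, p = 0.032 (smallest expected count 4 × 15/49 = 1.22; exact three-group p = 0.031)

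The two-arm Fisher test of 4/19 against 0/15 gives p = 0.113. Among completers every arm is 0/15, so there is nothing to test. The arithmetic is the same whichever arm holds the events.

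**The case against.** **Section 9.4.4 may mean everyone.** It speaks of *any* verified event and *any* participant above the YMRS threshold. Section 9.3 excludes non-completers from the analysis in the singular, and its sentence about all analyses only guarantees that completers are in. Section 9.4.2 names the per-protocol set although 9.3 already had, which suggests that 9.4.4 was left open. A reader might infer from 9.3 that the plan certainly discards these events. The documents do not support that certainty. What stands is that the only stated rule excludes them and no sentence says otherwise.

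**Participants are protected anyway.** A reader might infer that harms would go unmonitored. They would not. The SAE and TEAE suspension rules (7.4.1, 7.4.2) are based on enrollment, not completers. Adverse events are reviewed in real time (10.1.6). The DSMB gets blinded safety reports every 6 months and can see participants grouped by masked arm if there is reason (9.4.6). This objection holds in full for conduct of the trial, but none of it is the final arm comparison.

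**The loss would leave a trace.** Replacement and code reuse might suggest that a stopped participant disappears from view. Sections 7.2 and 9.3 require withdrawal reasons to be recorded, and Section 9.4.6 shows that participants have identification numbers that can be listed by arm. Stopping stimulation is also not the same as leaving the study (7.1), so replacement is not automatic. The records survive; the question is whether the final analysis uses them.

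**Events may be few, and not on active treatment.** Eligibility requires low suicide risk and no current mania, and excludes bipolar history. The only prior counts in the documents (2.3.1) are 4 sham participants with increased suicidal thoughts and no increase in ideation on tACS, in a similar depression study. A reader might infer that the rule would hide harm from theta-tACS. It could equally hide an excess on sham. With three or fewer events in one arm, the illustrated chi-square test would not reach 0.05 even with everyone included.

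**Conclusion.** The point holds as a defect of the final between-arm safety comparison. Section 9.3 states a completers-only rule, Section 9.4.4 offers no other, and several of the compared events are themselves reasons for not completing. Applied as written, the rule takes early-stopping events and the matching side-effect scores out of the comparison.

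Its size is unknown, because the documents give neither the rate nor the timing of stops for harm. In the illustration, an arm's observed rate falls from 21.1% to anything between 16.7% and 0%, depending on how many of the four events stop stimulation early, and does not change if none does. This rests on 15 completers per arm, four events in one arm and, for the test, none in the other two. The direction is open.

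The point does not reach the primary EEG analysis or participant protection during the trial. It should be corrected before data are unblinded, so that the choice between the two readings is not made with results in view.

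**What to change.** Add one sentence each to Sections 9.3 and 9.4.4: all safety analyses use every participant who received any stimulation, by arm received, counted by participant rather than by device code, since codes can be reused. Run the existing 9.4.4 comparisons in that set. Keep the per-protocol set for the EEG analysis in 9.4.2.

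A useful optional addition is one descriptive table by arm, with exact 95% intervals, of participants with at least one AE, SAE or TEAE and of those whose stimulation was stopped for harm.

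No new data are needed. The cost is slightly more analysis work and wide intervals: no events in 15 participants is still compatible with a risk of up to 21.8%, so the table would describe rather than test.
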